4.1.2.1 Use of Blinded RT-CGM by Control Group

After the 13 and 26-week visits, the Control Group will use the same blinded RT-CGM that was used at baseline for approximately one week. Instructions will again be provided for fingerstick testing on the HGM at least 4 times each day and as needed for calibration of the sensor.

Subjects will return one week after each visit to return the RT-CGM. The blinded RT-CGM will be downloaded by personnel not involved with treatment of the subject. Subjects who do not obtain at least 96 hours of RT-CGM glucose values with at least 24 hours of glucose values during the hours of 10 p.m. and 6 a.m. will be asked to repeat use of the blinded RT-CGM so that a sufficient amount of blinded data are obtained.

4.2 Follow-up Visits and Phone Contacts

The schedule for follow-up visits and phone contacts is the same for both treatment groups with the exception of a visit following the 13-week and 26-week visits for the Control Group to return the blinded RT-CGM (no study procedures will be completed at these visits).

A primary purpose of the visits and contacts will be to review diabetes management and make adjustments as needed.

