433 use the protocol-developed algorithms for how to make changes to diabetes management based
434 on HGM data.
- 435 4. Both groups will have follow-up visits at 1, 4, 8, 13, 19, and 26 weeks (± 1 week) plus one phone
436 contact between each visit (including one phone contact between randomization and the one week
437 visit) to review their diabetes management.
- 438 • Both groups will download device data on a weekly basis (if the subject has a computer).
439 Subjects with email access will be instructed to email the downloaded data to the clinical center
440 prior to each phone contact.
- 441 • For both groups, at each visit, the HGM and pump (if subject uses an insulin pump) will be
442 downloaded and for the RT-CGM Group, the RT-CGM will be downloaded.
- 443 6. In the 13th and 26th weeks, the Control Group will use a blinded RT-CGM for one week. The RT-
444 CGM Group will continue to use the unblinded RT-CGM. The Control Group will return the
445 blinded RT-CGM to the clinic after a week. The data will be reviewed by personnel who are not
446 involved in the care of the subject to determine if additional blinded sensor data are needed. The
447 blinded data will not be reviewed by study personnel for management decisions until the end of the
448 first 6 months of the study.
- 449 7. Following the 26-week visit:
- 450 • Subjects in the RT-CGM Group will continue to use the RT-CGM.
- 451 • Subjects in the Control Group will be provided with a RT-CGM and sensors after the week of
452 blinded use and will have visits after 1 week and 4 weeks, with a phone contact during the first
453 and third weeks.
- 454 • Both groups will have visits after 13 weeks and 26 weeks (study time 9 and 12 months).
- 455 ➤ At the 26-week visit (study time 12 months), subjects using the FreeStyle Navigator will
456 be given the choice to continue in the study until the device is approved by the FDA or
457 until Abbott Diabetes Care can no longer provide supplies for the study. Subjects who
458 agree to continue in the study will sign an addendum to the informed consent.
- 459 ▪ Subjects who continue in the study will return to the clinic every 3 months for a
460 standard clinic visit.

461
462 **1.7 General Considerations**

463 The study is being conducted in compliance with the policies described in the study policies document,
464 with the ethical principles that have their origin in the Declaration of Helsinki, with the protocol

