619 Enrolled subjects will return 10 (+3) days after enrollment for baseline testing and randomization. The
620 purpose of the visit will include the following:

- 621 • Assessment of compliance with the use of the RT-CGM and HGM
- 622 • Assessment of skin reaction in areas where a RT-CGM sensor was worn
- 623 • Randomization to the RT-CGM Group or the Control Group
- 624 • For subjects in the RT-CGM Group, initiation of unblinded RT-CGM use
- 625 • Instruction on downloading of glucose data for those with a home computer
- 626 • Collection of blood sample to send to the central laboratory for HbA1c determination

627
628 **3.2 Review of RT-CGM and HGM Data**

629 The HGM and RT-CGM data will be downloaded and reviewed by personnel not involved with treatment
630 of the subject to assess whether the subject has been compliant.

- 631 • To be continued in the study, it will be necessary that the subject has completed at least 3 HGM
632 measurements a day since enrollment, has used the RT-CGM on at least 6 out of 7 days prior to
633 the visit, and obtained at least 96 hours of RT-CGM glucose values with at least 24 hours of
634 glucose values during the hours of 10 p.m. and 6 a.m.

635
636 Subjects not meeting these criteria may be given a second opportunity at investigator discretion to
637 complete the RT-CGM and HGM requirements.

638
639 Subjects who are unable to meet the RT-CGM and HGM compliance requirements will be withdrawn
640 from the study and not randomized.

641
642 **3.3 Randomization**

643 Subjects who have been compliant with home glucose monitoring and use of the RT-CGM will be
644 randomized to one of two treatment groups:

- 645 1. RT-CGM Group
- 646 2. Control Group

647
648 The subject's randomization group assignment is determined by entering the Randomization Visit data on
649 the study website.

- 650 • The Jaeb Center will construct a Master Randomization List using a permuted block design.
- 651 • For subjects with baseline HbA1c $\geq 7.0\%$, the randomization will be stratified by clinical center,
652 age (8-<15, 15-<25, ≥ 25) and HbA1c (7.0-8.0, 8.1-10.0).
- 653 • For subjects with baseline HbA1c $< 7.0\%$, the randomization will be stratified by clinical center
654 only.

655
656 *Once a subject is randomized that subject will be included in the data analysis regardless of whether or*
657 *not the protocol for the assigned randomization group is followed. Thus, the investigator must not*

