4.2.1 Follow-up Visits

746 Follow-up visits will occur at

- 747 • 1 week (\pm 2 days)
- 748 • 4 weeks (\pm 1 week)
- 749 • 8 weeks (\pm 1 week)
- 750 • 13 weeks (\pm 1 week)
- 751 • 19 weeks (\pm 1 week)
- 752 • 26 weeks (\pm 1 week)

753

754 **4.2.1.1 Procedures at Follow-up Visits**

755 The following procedures will be performed in both groups at each visit, unless otherwise specified:

- 756 • Assessment of compliance with RT-CGM and HGM use
- 757 • Skin assessment (RT-CGM Group)
- 758 • Review of glucose data and pump data (if available) and recommendations for changes in diabetes management
- 759
- 760 • Collection of data for cost-effectiveness analysis
- 761 • HbA1c determination using the DCA2000 or similar point of care device for management decisions (4 weeks, 8 weeks, 13 weeks, 19 weeks and 26 weeks)
- 762
- 763 • Collection of a blood sample to send to the central laboratory for HbA1c determination (13 weeks, 26 weeks)
- 764
- 765 • Completion of Algorithm Satisfaction Questionnaire (4 weeks and 13 weeks)
- 766 • Completion of questionnaires (26 weeks)
 - 767 ○ **Subjects <18 Years Old**
 - 768 • Blood Glucose Monitoring System Rating Questionnaire
 - 769 • Peds-QL (combined sections of generic / diabetes modules)
 - 770 • Hypoglycemia Fear Survey
 - 771 • CGM Satisfaction Scale (RT-CGM Group Only)
 - 772
 - 773 ○ **Parents of Minor Subject**
 - 774 • Blood Glucose Monitoring System Rating Questionnaire
 - 775 • Peds-QL (combined sections of generic / diabetes modules)
 - 776 • Problem Areas in Diabetes (PAID - Parent version)
 - 777 • Hypoglycemia Fear Survey
 - 778 • CGM Satisfaction Scale (RT-CGM Group Only)
 - 779
 - 780 ○ **Subjects \geq 18 Years Old**
 - 781 • Blood Glucose Monitoring System Rating Questionnaire
 - 782 • Problem Areas in Diabetes (PAID)
 - 783 • SF-12
 - 784 • Hypoglycemia Fear Survey
 - 785 • CGM Satisfaction Scale (RT-CGM Group Only)
 - 786

787 **4.2.2 Phone Contacts**

788 A phone contact will be made between each protocol visit at the following times:

- 789 • 3 days (\pm 1 day)
- 790 • 18 days (\pm 3 days)
- 791 • 6 weeks (\pm 1 week)
- 792 • 10 weeks (\pm 1 week)
- 793 • 16 weeks (\pm 1 week)

- 22 weeks (± 1 week)

CHAPTER 5
POST-RANDOMIZED TRIAL OBSERVATION PHASE

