935 post-RCT observational phase. The number of questions may be reduced prior to initiation of its use in
936 the study. A version of this questionnaire will also be completed by the spouses of adult subjects in the
937 RT-CGM group following the 26-week visit of the RCT and by spouses of adult subjects in both groups
938 following the 26-week visit of the post-RCT observational phase. For spouses, the questionnaire will be
939 completed on paper at home and mailed back to the clinical center. Administration time is approximately
940 10-20 minutes.

941
942 **6.9 Algorithm Satisfaction Questionnaire**

943 This questionnaire was developed to measure the frequency and convenience of use of study-developed
944 algorithms and satisfaction with use of the algorithms developed for the protocol. A separate
945 questionnaire will be completed by the RT-CGM Group and the Control Group at 4 weeks and 13 weeks.
946 The Control Group will complete the RT-CGM Algorithm Satisfaction Questionnaire at 4 weeks in the
947 post-RCT observational phase. Data from this study will be used to evaluate the measure's psychometric
948 properties including internal consistency, parent-adolescent agreement, associations with study outcomes
949 and descriptive statistics. Administration time is approximately 5 minutes.

950
951

952 **CHAPTER 7**
953 **ADVERSE EVENTS**

954
955 **7.1 Definition**

956 A reportable adverse event is any untoward medical occurrence that meets criteria for a serious adverse
957 event or any unexpected medical occurrence in a study subject that is study or device-related.

958 **7.2 Recording of Adverse Events**

959 Throughout the course of the study, all efforts will be made to remain alert to possible adverse events or
960 untoward findings. The first concern will be the safety of the subject, and appropriate medical
961 intervention will be made.

962
963 The investigator will elicit reports of adverse events from the subject at each visit and complete all
964 adverse event forms online. Each adverse event form is reviewed by the Coordinating Center to verify the
965 coding and the reporting that is required.

966
967 The study investigator will assess the relationship of any adverse event to be related or unrelated by
968 determining if there is a reasonable possibility that the adverse event may have been caused by the study
969 device or study procedures.

970

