971 The intensity of adverse events will be rated on a three-point scale: (1) mild, (2) moderate, or (3) severe. It
972 is emphasized that the term severe is a measure of intensity: thus a severe adverse event is not necessarily
973 serious. For example, itching for several days may be rated as severe, but may not be clinically serious.

974
975 Adverse events will be coded using the MedDRA dictionary.

976
977 Definitions of relationship and intensity are listed on the website data entry form.

978
979 Adverse events that continue after the subject's discontinuation or completion of the study will be
980 followed until their medical outcome is determined or until no further change in the condition is expected.

981
982 **7.3 Reporting Serious or Unexpected Adverse Events**

983 A serious adverse event is any untoward occurrence that:

- 984
- 985 • Results in death
 - 986 • Is life-threatening; (a non life-threatening event which, had it been more severe, might have become
987 life-threatening, is not necessarily considered a serious adverse event)
 - 988 • Requires inpatient hospitalization or prolongation of existing hospitalization
 - 989 • Results in significant disability/incapacity
 - 990 • Is a congenital anomaly/birth defect

991 An *Unanticipated Adverse Device Event* is defined as an adverse event caused by, or associated with, a
992 device, if that effect or problem was not previously identified in nature, severity, or degree of incidence.

993
994 Serious or unexpected adverse events must be reported to the Coordinating Center immediately via
995 completion of the online serious adverse event form.
996

997 The Coordinating Center will notify all participating investigators of any adverse event that is both
998 serious and unexpected. Notification will be made within 10 days after the Coordinating Center becomes
999 aware of the event.

1000
1001 Each principal investigator is responsible for informing his/her IRB of serious study-related adverse
1002 events and abiding by any other reporting requirements specific to their IRB.
1003

1004 **7.4 Risks And Discomforts**

1005 **7.4.1 Skin Reactions**

1006 There is a low risk for developing a local skin infection at the site of the sensor needle placement.
1007 Itchiness, redness, bleeding, and bruising at the insertion site may occur as well as local tape allergies.
1008

1009 During each follow-up visit, each site where a RT-CGM sensor has been worn will be assessed by study

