1010 personnel. Both acute and non-acute changes will be assessed (as described on the case report form and
1011 in the Procedures Manual). If a skin reaction is classified as severe (the observation is extremely
1012 noticeable and bothersome to subject and may indicate infection or risk of infection or potentially life-
1013 threatening allergic reaction) an Adverse Event Form will be completed.
1014

1015 **7.4.2 Fingertick Blood Glucose Measurements**

1016 Fingerticks may produce pain and/or ecchymosis at the site.
1017

1018 **7.4.3 Psychosocial Questionnaires**

1019 As part of the study, subjects and parents will complete psychosocial questionnaires which include
1020 questions about their private attitudes, feelings and behavior related to diabetes. It is possible that some
1021 people may find these questionnaires to be mildly upsetting. Similar questionnaires have been used in
1022 previous research and these types of reactions have been uncommon.
1023

1024 The study may include other risks that are unknown at this time.
1025

1026 **7.5 Data and Safety Monitoring Board**

1027 An independent Data and Safety Monitoring Board will be informed of all serious adverse events and any
1028 unanticipated adverse device events that occur during the study and will review compiled adverse event
1029 data at periodic intervals.
1030

1031 **CHAPTER 8**
1032 **MISCELLANEOUS CONSIDERATIONS**

1033
1034 **8.1 Benefits**

1035 It is expected that RT-CGM devices will have an important role in the management of diabetes.
1036 Therefore, the results of this study are likely to be beneficial for patients with diabetes.
1037

1038 It is possible that subjects will not directly benefit from being a part of this study. However, it is also
1039 possible that the blood sugar information from the monitor along with the algorithms provided for
1040 management decisions will be useful for subjects' diabetes self-management.
1041

1042 **8.2 Subject/Parent Reimbursement**

1043 The study will provide the RT-CGM and related supplies, and the study HGM and test strips.
1044

1045 The study will be paying the subject \$25 per completed protocol-required visit to cover travel and other
1046 visit-related expenses. Additional travel expenses will be paid in select cases for subjects with higher
1047 expenses. There will be no compensation for completing telephone calls.
1048

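### Section 4.2.1.1 limits skin assessment to the RT-CGM Group, against 7.4.1 and the schedule table, and 4.2 has no examination when controls return a just-worn sensor, so their skin reactions can be missed or seen late

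*Protocol*

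**What the plan says.** Protocol section 7.4.1 states the general rule: "During each follow-up visit, each site where a RT-CGM sensor has been worn will be assessed by study" personnel. It adds "Both acute and non-acute changes will be assessed" and names no treatment group. A reaction classified as severe leads to an Adverse Event Form. The schedule table in 1.6.1 F marks skin assessment at weeks 0, 1, 4, 8, 13, 19 and 26, also without an arm limit. The same table does footnote another row, the CGM Satisfaction Scale, as applying to the RT-CGM Group alone.

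Section 4.2.1.1, which lists procedures at randomized-phase visits, reads differently: "Skin assessment (RT-CGM Group" only.

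Controls wear a blinded sensor for about a week after the 13- and 26-week visits (4.1.2.1). Then "Subjects will return one week after each visit to return the RT-CGM". Section 4.2 says of these return visits that "no study procedures will be completed at these visits". Section 7.2 says: "The investigator will elicit reports of adverse events from the subject at each visit and complete all" adverse event forms. After the baseline blinded week, by contrast, section 3.1 lists "Assessment of skin reaction in areas where a RT-CGM sensor was worn" among the purposes of the randomization visit, so both arms are examined after that wear.

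Section 1.6.2 then has controls move to unblinded use: "Subjects in the Control Group will be provided with a RT-CGM and sensors after the week of" blinded wear.

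**The concern.** A site cannot follow 4.2.1.1 and also follow 7.4.1 and the table. Different sites may settle the conflict differently, and the skin findings would then depend on which section each site read.

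The return visit is also the one occasion on which control sensor sites are fresh, and the protocol writes no examination for it. The skin assessment is what triggers an Adverse Event Form for a severe reaction. Without it, capture in controls depends on the subject's own report or on a later look. The instruction to contact staff about a skin reaction appears in section 3.4 for the RT-CGM Group and has no counterpart in section 3.5 for the Control Group.

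At stake are the completeness of the skin tabulations promised in 9.2.1.1, the adverse event data that go to the safety board, and the record of how a control tolerated the sensor before ongoing wear begins.

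**Working it through.** The plan gives no figure to reproduce. The check sets the sections side by side and follows the timeline.

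**Which instruction covers controls in the randomized phase**

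| Source | Control skin assessment |
|---|---|
| 7.4.1 | Yes, every worn site at each follow-up visit |
| 1.6.1 F table | Yes, no arm limit |
| 4.2.1.1 | No, RT-CGM Group only |
| 4.2, return visits | No procedures of any kind |
| 3.1, after baseline wear | Yes, both arms |

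**Wear after the 13-week visit.** The visit window is 13 ± 1 weeks and the wear lasts about one week, so removal falls between 12 + 1 = 13 and 14 + 1 = 15 weeks. The assessment marked at week 13 precedes this wear and cannot see it.
- Under 4.2.1.1, there is no examination in the rest of the randomized phase.
- Under the table, the next mark is week 19 ± 1, that is weeks 18 to 20. The shortest delay is 18 − 15 = 3 weeks and the longest is 20 − 13 = 7 weeks. At nominal times it is 19 − 14 = 5 weeks.

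**Wear after the 26-week visit.** Removal is at about week 27, when unblinded RT-CGM is issued. Section 5.3 and the observation-phase table give the next skin assessment at the 1-week visit (± 2 days). Counting that visit from the issue of the device, as 1.6.2 reads, the first look is about one week into ongoing use.

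**Extent at minimum enrolment**
- Controls: 330/2 = 165 in the primary cohort and 120/2 = 60 in the secondary cohort, which has an identical protocol. 165 + 60 = 225.
- Wear: 225 × 2 = 450 subject-weeks, before dropout and before any repeat wear requested under 4.1.2.1.

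**Likely number of severe reactions.** The documents give no rate for a single week of wear. The pilot (1.3) reports severe skin reactions in 2 of 30 subjects, 2/30 = 6.7%, over 13 weeks at 134 to 149 hours of use per week. If the weekly risk were constant, which is an assumption, the rate would be 2/(30 × 13) = 0.5% per week, and 450 × 2/390 = 2.3 severe reactions over all the wear in question. With only two events behind it, this shows no more than that the number is probably small and not plainly zero.

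**The case against.** The strongest case against this is that the matter is a drafting slip with limited consequence. Several parts of that case stand.

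- **A reader might infer that section 4.2 directly breaches 7.4.1.** It does not, read literally. Section 7.4.1 speaks of follow-up visits, and 4.2.1 lists these as weeks 1, 4, 8, 13, 19 and 26. The return visit is not among them. The plain contradiction is 4.2.1.1 against 7.4.1 and the table. The return visit is a gap beside it.
- **A reader might infer that control skin reactions are missed.** The text supports only that they can be missed or seen late. Adverse events are elicited at later visits, the table (if it governs) gives a week-19 check, and the first observation-phase visit includes one. A severe reaction, as 7.4.1 describes it, is also the kind a subject is likely to mention when asked.
- **The conflict with 7.2 is arguable.** Section 4.1.2.1 has the returned device downloaded and its data checked, so the bar on procedures cannot be absolute and need not switch off the general duty to ask about adverse events. That is a reason to clarify the sentence, since a site may well take it at its word.
- **A reader might infer a biased comparison of reaction rates per sensor worn.** Section 9.2.1.1 plans no such comparison. It promises tabulations for visits at which an assessment was made.
- **A reader might apply the pilot's 6.7% to these wears.** That figure covers 13 weeks of near-continuous use, and both affected subjects resumed wear once the reaction had resolved.
- **Controls are not new to the sensor.** All had a baseline week of wear and a skin assessment before randomization.

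None of this reconciles 4.2.1.1 with 7.4.1 and the table, or explains why the same one-week wear is examined at baseline and not at weeks 13 and 26.

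**Conclusion.** The concern holds as an internal contradiction with a related gap in safety ascertainment. Followed as written, 4.2.1.1 and 4.2 leave the 13-week control wear unexamined in the randomized phase, and controls begin ongoing wear after week 26 without a prior skin check. If the table governs instead, the first look at the 13-week wear comes 3 to 7 weeks after removal.

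The exposure is about 450 subject-weeks in about 225 controls. This rests on minimum enrolment, equal allocation, two wears per control and no dropout. The delay rests on the stated visit windows, and the one-week figure for the second wear on counting the observation-phase visit from the issue of the unblinded device. The expected number of severe reactions is unknown and probably small.

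The effect is confined to the skin tabulations and skin-related adverse event capture. The HbA1c analysis, power and type I error are untouched. The point should be corrected, but it does not threaten the trial's main conclusion. The Procedures Manual, to which 7.4.1 refers for detail, is not at hand and may already settle practice. The protocol text would still need to agree with it.

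**What to change.** 1. In 4.2.1.1, remove the restriction to the RT-CGM Group so that skin assessment applies to any subject who has worn a sensor, in line with 7.4.1 and the 1.6.1 F table.
2. In 4.2, replace the statement that no study procedures are completed with one saying that the existing skin assessment and adverse event elicitation are done when controls return the blinded sensor after weeks 13 and 26, including any return after a repeat wear.
3. Add the two return visits to the schedule table in 1.6.1 F.

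The cost is a protocol amendment and a few minutes per control at a visit already attended, using the existing skin form. Staff able to complete that form must be present. Looking at the skin reveals no glucose data, so the blinding of the sensor readings is not affected.
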